3. OBJECTIVES AND ENDPOINTS

The objectives and corresponding endpoints are provided in [Table 8](#).

Table 8 Objectives and Endpoints

Objectives	Endpoints
Primary	

 To determine the maximum-tolerated dose (MTD) and/or the optimal biological dose (OBD) for intravenous (IV) and subcutaneous (SC) administrations of RO7172508 as monotherapy and with obinutuzumab pre-treatment (if applicable) To assess the safety and tolerability profile of RO7172508 and with obinutuzumab pre-treatment (if applicable) 	
 Nature and frequency of dose-limiting toxicities (DLTs) and other AEs, PD and PK profile Incidence, nature and severity of AEs graded according to the National Cancer Institute (NCI) Common Terminology Criteria for Adverse Events (CTCAE) v5.0
Secondary	

 To establish the IV and SC pharmacokinetics of RO7172508 given as monotherapy and with obinutuzumab pre-treatment (if applicable) 	
The PK profiles and parameters derived for RO7172508 including where appropriate and when data allow, the parameters listed below:
 
 Maximum concentration (C_{max}) Time of maximum concentration (T_{max}) Clearance (CL) or apparent clearance (CL/F) (dependent on route of administration) Volume of distribution at steady state (V_{ss}) Area under the curve (AUC) Half-life ($t_{1/2}$) Other PK parameters may be determined, as deemed appropriate.

 To assess the incidence of anti-drug antibodies (ADAs) against RO7172508 with obinutuzumab pre-treatment (if applicable) 	
 Presence or absence and titer of ADAs

 To characterize PD effects and duration of PD response for multiple doses and schedules of RO7172508 administration 	
 Changes in frequency, activation status and spatial distribution of tumor infiltrating lymphocytes (TILs).

Table 8 Objectives and Endpoints (cont.)

Objectives	Endpoints
Secondary (cont.)	

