If at the end of the dose escalation, the criteria to implement obinutuzumab pretreatment has not been met and at the same time, there is low confidence (i.e. <70% confidence level) that the true rate of loss of exposure is < 5%, then additional participants will be enrolled (see [Appendix 8](#)). Participants will then be randomized to cohorts at the OBD with or without obinutuzumab to further evaluate the safety and PK profile.

The need of obinutuzumab for further clinical development of RO7172508 will be determined based on the overall assessment of safety and PK data as well as pharmacodynamics effects.

Figure 5 *Decision Tree at End of Dose Escalation*

The total number of participants with relevant loss of exposure required to meet the criteria at subsequent evaluations, will depend on the actual number of participants enrolled and on the number of cohorts necessary to complete the dose escalation. For operating characteristics see [Appendix 8](#).

Independent from loss of exposure, obinutuzumab pretreatment will be initiated if there is evidence of ADA-mediated hypersensitivity reactions or other safety signals that are likely related to ADAs. In such instance, obinutuzumab will be implemented for all subsequent participants and the enrollment of participants without obinutuzumab will be stopped.

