8.5.1 Immunogenicity Assessments

As RO7172508 is a human antibody, there is a risk that ADAs against RO7172508 could develop, potentially reducing its efficacy and/or potentially resulting in symptomatic hypersensitivity reaction, in particular immune-complex reactions.

Antibodies to RO7172508 will be evaluated in blood samples collected from all participants according to the SoA (Section 1.3). Additional ADA samples should also be collected at the time of treatment discontinuation or at the safety follow-up visit. In each case, for each collected ADA sample, a corresponding PK sample will be collected at the same time-point for the determination of the RO7172508 concentration. *Participants experiencing a Grade ≥ 3 toxicity potentially related to ADAs will not be further treated with RO7172508 (see Section 7.1).*

Validated screening, confirmatory, and titer assays will be employed to detect ADAs against RO7172508. The date and time of each sample will be recorded in the eCRF.

Remaining volumes of ADA samples may also be used for assay development or validation, for compound-related exploratory analyses, or to help develop further blood tests, after they are used for the mentioned intended uses.

Antibodies to obinutuzumab will be evaluated in all participants who receive obinutuzumab as pre-treatment according to the SoA.

The PK/ADA samples will be destroyed within 2 years after the date of final CSR, unless the participant agrees to participate in the RBR.

Details on sampling procedures, sample storage, and shipment are given in the Study Flow Chart and Laboratory Manual.

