9.3 POPULATIONS FOR ANALYSES

For purposes of analysis, the following populations are defined in [Table 21](#).

Table 21 Analysis Populations

Population	Description
Efficacy	All participants who received at least one dose of RO7172508.
Safety	All participants enrolled in the study who received at least one dose of study treatment (RO7172508 and/or obinutuzumab if applicable) will be included in the safety population. Unless otherwise specified, the safety population will be the default analysis set used for all analyses.
DLT evaluable	DLT-evaluable participants are those who have completed the DLT window without a DLT, or participants who reported with a DLT. This population will be used in the determination of the MTD.
Pharmacokinetic	All participants who have received at least one dose of study treatment and who have data from at least one post-dose sample will be included in the PK analysis population. Participants will be excluded from the PK analysis population if they significantly violate the inclusion or exclusion criteria, deviate significantly from the protocol, or if data are unavailable or incomplete which may influence the PK analysis. Excluded cases will be documented together with the reason for exclusion. All decisions on exclusions from the analysis will be made prior to database closure.
Immunogenicity	Participants who had at least one pre-dose and one post-dose ADA assessment will be included and analyzed according to the treatment they actually received. The relationship between ADA status and safety, efficacy, PK, and biomarker endpoints will be analyzed and reported descriptively via subgroup analyses.

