9.4.2 Efficacy Analyses

The primary and secondary efficacy analyses will include all participants in the efficacy population with participants grouped according to cohort (and schedule if applicable) within each study part. Primary, secondary, and exploratory endpoints are described in Section 3.

The efficacy endpoints of ORR, DCR and PFS according to RECIST v1.1 will be evaluated using the methods described in [Table 22](#):

- Objective response is defined as a CR or PR, as determined by the Investigator's assessment using RECIST v1.1 and confirmed by repeat assessments ≥ 4 weeks after initial documentation. To classify a response as SD, measurements will have to be classified as stable (according to RECIST v1.1) at least once after study entry at a minimum of 6 weeks after study entry.
- ORR and DCR are both determined as the rate of participants with an observed tumor response of CR or PR (ORR) or CR, PR or SD (DCR). ORR and DCR will be derived for RECIST v1.1.
- Among participants with an objective response (responders), DOR will be defined as the time from first occurrence of a documented objective response until the time of documented disease progression or death within 30 days from last study treatment from any cause during treatment, whichever occurs first. Censoring methods will be

the same as the one applied for PFS (on-study drug treatment). This will be calculated for participants who have a best overall response of CR or PR as defined per RECIST v1.1 and per iRECIST.

- PFS (on-treatment) will be defined as the time from study treatment initiation (Cycle 1 Day 1) to the first occurrence of documented disease progression or death from any cause during treatment (death within 30 days from last study treatment), whichever occurs first. For participants who do not have documented progressive disease or death during the study, PFS will be censored at the day of the last tumor assessment. If no post study drug treatment tumor assessment is available, PFS will be censored at the day of the first study drug administration + 1 day.
- OS is defined as the time from the first dose of study treatment to the time of death from any cause on study. Participants who are still alive at the time of analysis will be censored at the time of their last study assessment (for active participants) or at the last date known alive (for participants in follow-up).

Table 22 Efficacy Statistical Analysis Methods

Endpoint	Statistical Analysis Methods

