9.4.5 Immunogenicity Analyses

Antibodies to RO7172508 will be evaluated in blood samples collected from all participants using appropriate assays.

Listings and/or summaries will be prepared for results from screening, confirmatory, and/or titer assays employed to detect ADAs against to RO7172508.

Monitoring and characterization of ADA responses and their potential impact on PK, PD, safety, and efficacy of RO7172508 will also be investigated.

Antibodies to obinutuzumab will be evaluated in blood samples using appropriate assays from all participants who receive obinutuzumab as pre-treatment.

Additional analyses may be conducted as appropriate.

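### Efficacy and safety by ADA status are planned as plain subgroups on a status that is fixed only after dosing, which distorts the PFS and OS contrast in favour of ADA-positives and distorts crude AE incidence as well

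*Combined protocol and SAP*

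**What the plan says.** The immunogenicity row of Table 21 (Section 9.3) sets the population and the method together. "Participants who had at least one pre-dose and one post-dose ADA assessment will be included and analyzed according to the treatment they actually received", and then: "The relationship between ADA status and safety, efficacy, PK, and biomarker endpoints will be analyzed and reported descriptively via subgroup analyses". Section 9.4.5 adds "Monitoring and characterization of ADA responses and their potential impact on PK, PD, safety, and efficacy of RO7172508 will also be investigated" and "Additional analyses may be conducted as appropriate", without naming a method. The endpoint in Section 3 is "Presence or absence and titer of ADAs". The documents do not say whether status means ever-positive, treatment-emergent or positive at a given visit, and they define no onset date.

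On the outcome side, Section 9.4.2 states that "PFS (on-treatment) will be defined as the time from study treatment initiation (Cycle 1 Day 1) to the first occurrence of documented disease progression". A death on treatment counts as an event too, and OS also runs from the first dose. Section 8.3.1 collects AEs until 90 days after the last dose, so the time at risk grows with time on treatment. On sampling, Section 8.5.1 says "Additional ADA samples should also be collected at the time of treatment discontinuation or at the safety follow-up visit", and the schedules of activities list ADA at both the end-of-treatment visit and the 60-day safety follow-up. No landmark, time-dependent or exposure-adjusted analysis by ADA status appears anywhere.

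**The concern.** A participant can be classed as ADA-positive only by staying under observation long enough to convert and be sampled. Under an ever-positive rule, the time from Cycle 1 Day 1 to conversion is credited to the positive group, although nobody in that group could have left follow-up during it. Early progressors and early deaths collect in the negative group for the same reason. This is immortal-time bias, and it arises even when ADAs have no effect at all. AE counts carry the mirror image: the group followed longer has more time to report an event.

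The protocol takes ADAs seriously. Section 8.3.8.4 notes severe ADA-associated events, two of them fatal, with the in-class agent cibisatamab. If the planned tables cannot separate an ADA effect from length of follow-up, the trial cannot say whether ADAs affect efficacy or tolerability.

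**Working it through.** The plan gives no sample size, power or effect size for this comparison, so there is no figure of its own to reproduce. The size was obtained by simulation, with one case also worked by hand.

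**Inputs from the documents.** Eventual ADA-positive proportion 0.67: Appendix 8, Section 2.1 reports ADA-related loss of exposure in 14 of 21 on cibisatamab, used here as a stand-in. Follow-up is capped at 24 months of treatment (Section 4.1.1). The last ADA sample is at end of treatment, or at the 60-day safety follow-up.

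**Assumptions not in the documents.** Exponential PFS with median 60, 90 or 120 days. ADA onset with a 7-day minimum, exponential thereafter, median 21, 42 or 84 days, independent of prognosis. Treatment ends at progression. Hazard ratio after onset 1.0, 1.5 or 2.0. AEs at 1 per 60 days on treatment in everyone.

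**Worked case (median PFS 90, median onset 42, no ADA effect, status at end of treatment):**
- Progression rate μ = ln2/90 = 0.00770; onset rate λ = ln2/(42 − 7) = 0.01980.
- Proportion positive = 0.67 × exp(−7μ) × λ/(λ + μ) = 0.67 × 0.9475 × 0.7200 = 0.457.
- Mean onset among converters = 7 + 1/(λ + μ) = 7 + 36.4 = 43.4 days.
- After onset the remaining time still averages 1/μ = 129.8 days, so mean PFS in positives = 43.4 + 129.8 = 173.2 days.
- Mean PFS in negatives = (129.84 − 0.4571 × 173.20)/(1 − 0.4571) = 93.3 days.
- Crude hazard ratio = 93.3/173.2 = 0.54. The 24-month cap is negligible here.

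The simulation (400,000 participants per scenario) gives the same 0.54, with medians of 136 versus 52 days and 91% versus 56% progression-free at 6 weeks. Counting the 60-day sample moves it to 0.81, with medians of 102 versus 72 days.

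**Crude PFS hazard ratio, ADA-positive versus ADA-negative, nine scenarios per cell:**

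| True HR after onset | Status at end of treatment | 60-day sample counted |
|---|---|---|
| 1.0 | 0.47-0.70 | 0.66-0.98 |
| 1.5 | 0.58-0.98 (nine of nine below 1) | 0.80-1.36 (three below 1, one at 1.00) |
| 2.0 | 0.67-1.24 (seven of nine below 1) | 0.88-1.71 (three below 1) |

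Every value lies below the truth.

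**Alternatives on the same data:**

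| True HR | Time-dependent status | Day-42 landmark (about Cycle 3 Day 1) |
|---|---|---|
| 1.0 | 1.00-1.01 | 0.99-1.01 |
| 1.5 | 1.49-1.51 | 1.30-1.39 |
| 2.0 | 1.99-2.01 | 1.61-1.79 |

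The landmark removes the artefact but dilutes harm, because later converters stay in its negative group.

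**AEs, equal rates, no ADA effect.** At least one event in 71-89% of positives versus 47-65% of negatives (status at end of treatment), or 60-81% versus 53-73% (60-day sample). These count on-treatment events only. In the worked case they are 82% versus 57%. If the same rate ran on through the 90-day reporting tail, the no-event fractions would be multiplied by exp(−90/60) = 0.223, giving 1 − 0.18 × 0.223 = 96% versus 1 − 0.43 × 0.223 = 90%: narrower, same direction. The direction is not fixed once ADAs shorten PFS. With early onset (21 days) and the 60-day sample, positives show fewer events (for example 54% versus 58% at a true HR of 1.5 and median PFS of 60 days), although the AE rate is identical. Crude incidence tracks time on treatment, not AE risk.

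**The case against.** Four points can be made for the plan.

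- **Status is undefined, and 9.4.5 leaves room for other analyses.** True: ever-positive is inferred. But an open allowance for further work is not a specified method, and the missing definition is itself a gap.
- **Sampling continues after treatment, and Section 7.1 allows treatment beyond RECIST progression.** This stands in part. With early onset and the 60-day sample the null ratio is 0.97-0.98, close to unbiased. With later onset it is not, and participants who die early cannot give the later sample.
- **No testing and no hazard ratio are planned.** Correct: the ratios above only summarise the gap between curves. Descriptive Kaplan-Meier plots and AE tables carry the same distortion.
- **No stated decision depends on it.** This also stands. The obinutuzumab trigger in Section 4.1.3 is the rate of loss of exposure (Cmax at Cycle 3 against Cycle 1) or ADA-related safety signals. For later development, "The need of obinutuzumab for further clinical development of RO7172508 will be determined based on the overall assessment of safety and PK data", together with pharmacodynamics. Route selection in Section 9.4 uses ADA incidence and effect on exposure, and does not expect efficacy to be a key criterion. A reader might infer that the obinutuzumab decision will be wrong; the documents do not support that.

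A reader might also infer that ADA-positives will look better on safety as well as efficacy. The no-effect calculation shows the opposite for crude AE incidence.

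**Conclusion.** The point holds in a limited form. As written, the subgroup analysis sets an outcome clock that starts at first dose against a status that needs later follow-up. Under an ever-positive reading and no ADA effect, the PFS contrast favours ADA-positives: illustrative hazard ratio 0.47-0.70 with status at end of treatment, 0.66-0.98 with the 60-day sample. OS is distorted in the same direction by the same mechanism but was not sized. The figures rest on assumed PFS medians, assumed onset times independent of prognosis, and the 67% stand-in for the ADA rate.

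It would be tempting to say that ADAs will appear harmless or protective even if they do harm. That is too general. Harm is understated in all scenarios examined, but whether it is reversed depends on onset time, size of harm and which samples count. Because the analysis is exploratory and feeds no stated rule on efficacy, the damage is confined to what can be concluded about ADA impact on efficacy and safety. It is still worth correcting, since the samples needed are already scheduled.

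**What to change.** Amend Table 21 and Section 9.4.5 as follows.

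- **Definition.** State what makes a participant ADA-positive, including how a positive pre-dose sample is handled, and take the onset date as the first positive post-dose sample.
- **PFS and OS.** Treat ADA status as time-dependent: person-time event rates, and Kaplan-Meier curves in which a participant moves from the negative to the positive risk set at onset. Add a Cycle 3 Day 1 landmark as a sensitivity analysis, counting time from the landmark. State that it excludes anyone who progressed or left before it, including progressions at the first scan (due within 7 days before that visit), and that it dilutes later-onset effects.
- **AEs.** Report exposure-adjusted rates in ADA-negative and ADA-positive person-time within the same treatment period, for example Cycles 1-2 and Cycle 3 onward. Avoid crude ever/never incidence. Avoid also an unadjusted before/after comparison: Section 4.2.1 says cibisatamab toxicity fell mainly in the first days after the first dose, and Section 8.3.8.1 places IRRs typically in the first two cycles, so time before onset would hold most early toxicity and ADAs would look protective.
- **Response.** Show it by ADA status only with a note on the timing of conversion relative to response.

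The cost is SAP wording and programming, with no new samples or visits. Data will be sparse in small cohorts, so some of these summaries may be possible only after pooling cohorts.

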9.4 STATISTICAL ANALYSES

The data will be analyzed by the Sponsor and/or designated Contract Research Organization (CRO). Any data analysis carried out independently by the Investigator should be submitted to the Sponsor before publication or presentation. The data will be summarized with respect to demographic and baseline characteristics, efficacy observations and measurements, safety observations and measurements, pharmacokinetic and biomarker measurements. Data will be summarized by cohort and regimen within each part and CEA level where applicable, *including the additional participants that may be enrolled in expanded cohorts (see Section 4.1.2.2)*. *Participants who receive only obinutuzumab but no dose of RO7172508 will be summarized separately.*

The baseline value of any variable will be defined as the last available value prior to the first administration of study treatment (RO7172508 or obinutuzumab (if applicable) as appropriate).

The following endpoints may be used to select a route of administration for further development: PD parameters including T-cell activation in blood and in the tumor; pharmacokinetic parameters such as AUC, C_{max} and half-life; tolerability and safety; as well as incidence of ADAs and their effect on exposure. Clinical efficacy will be considered, but is not expected to be a key criterion, as efficacy will likely be affected by parameters which cannot be controlled for in such small cohorts. Data will be listed and summarized by dose group as described in this analysis section. Analyses are exploratory in nature and no formal hypothesis testing will be performed.

If one route of administration is not unequivocally superior, and a decision cannot be taken during or at the end of dose escalation, both routes of administration will be compared in disease specific expansion. Criteria for selection of a route of administration will then be added via the amendment preceding the expansions, including endpoints.

